standard (non-incentive) invitation only. For the sub-study, the standard invitation letter will be replaced with one of the 3 modified letters. All new participants will be randomized to receive one of the 3 letters during 2 predetermined rounds of invitations (involving n=2,124 individuals).

Rationale and plan for sub-study part 1: Over nearly 2 years of our prevention program, we have tested a systematic screening outreach strategy for increasing screening completion among uninsured patients, not up to date with screening. Through these carefully evaluated interventions, we have shown that our outreach invitation strategy, particularly when it includes FIT invitations, markedly increases screening completion among the uninsured. Indeed 36% of individuals invited to complete FIT return the test. While this rate of participation is substantial, it may be improved by making changes to our invitation letters. In 2 predetermined rounds of invitations (involving n=2,124 individuals), we will slightly modify the invitation letters to test our hypothesis that providing information in the letter about the value of the kit and attenuating concern about future cost will further increase FIT and follow-up response rates.

There will be 3 conditions for the invitation letter and individuals will be randomly assigned 1:1:1 to each condition. The 3 conditions contain just slight differences in the information provided in the letter, as follows: (i) a control invitation letter (similar to letters in previous studies with some slight wording and grammatical improvements, (ii) the control letter plus the addition of one line informing recipients of the average value of the procedure (~\$200), and (iii) a letter with the average value and a sentence assuring patients that should a follow-up test be requested, it will be provided free of charge.

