The addition of this pragmatic trial to the ongoing prevention program provides no additional risk to individuals and will allow us to assess a hypothesis that will contribute to our success in increasing screening completion rates among this population. From a statistical standpoint, assuming a control invitation letter response rate of 36% with the planned sample size of n=708 per group, we will have over 80% power to detect absolute increases of \geq 8% between the control invitation and the first alternate letter, as well as between the control invitation and the second alternate letter, assuming two-sided alpha=0.125 for each comparison.

Part 2): In part 2 of the sub-study, participants will receive their FIT responses in either a white envelope (normal results, no immediate follow-up necessary) or a red envelope (positive result, need to follow-up with doctor). The only change to this portion of the study is the color of the envelope patients receive.

Rationale and plan for part 2: With our current program, the rate of follow up to diagnostic colonoscopy after an abnormal FIT is 58%. Since indivdiuals with abnormal FIT have an increased chance of having colorectal cancer, identifying alternate strategies to improve compliance with diagnostic colonoscopy is desirable. Accordingly, we propose to employ a simple alerting tactic through the color of the envelope (red for abnormal and white for normal). We hypothesize that more people will follow-up after receiving a positive FIT result as a result of the messaging importance of abnormal tests with a red envelope. Because these changes will be employed in 2 predetermined rounds of invitations, we will have the opportunity to conduct an pre-post analysis of the follow-up rates to test our hypothesis that this alerting tactic will increase follow-up rates. From a statistical standpoint, pre-intervention, we assume there are at least 329 individuals with abnormal FIT, and that 58% (n=191) complete diagnostic colonoscopy. Post modification, we expect a minimum 107 patients with abnormal FIT. With these sample sizes, assuming two-sided alpha=0.05, we will have 80% power to detect a difference post intervention of \geq 14.9%.

Change in risks to participants

The sub-study does not substantially change risks to study participants. Accordingly, no change to our process for recruitment or waiver of informed consent for invitation is proposed.

Criteria for Inclusion of Subjects:

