we will even have 90% power to detect a smaller screening rate increase of \geq 5% (Power was computed with nQuery Advisor Software v.7.0).

Evaluation Aim B) Compare rates of initial and repeat screening completion among 1) Patients offered a modest financial incentive to complete screening, in addition to outreach invitations (n=2,000), vs. 2) Patients offered outreach invitations alone (n=~18,000). The rate of initial screening completion will be defined by:

Initial	# patients completing a FIT
Screening	Year 1
Completion Rate =	# of patients sent FIT invitation Year 1

We will compare the initial screening completion rate for patients offered the financial incentive, in addition to screening outreach, to the initial rate for patients offered screening outreach alone using a Chi-square test of proportions, with a 2-sided p value <0.05

considered statistically significant. The rate of repeat screening for Years 2 and 3 will be defined by:

Year 2	# patients completing FIT	Year 3 Repeat	# patients completing FIT
Repeat	screening Year 2	Completion	screening Year 3
Completion	# patients completing FIT Year 1	Rate =	# patients completing FIT Year 2
Rate =	with normal result		with normal result

We will compare initial FIT completion rates for the financial incentive plus organized outreach vs. organized outreach alone groups using a Chi-square test, with a 2-sided p value <0.05 considered statistically significant. The same approach will be taken for comparing repeat FIT completion rates for Years 2 and 3.

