Sample size for Evaluation Aim C. The sample size for Evaluation Aim C is based on comparing the initial screening participation rate between the \$5 vs. the \$10 incentive groups. As is outlined in Section A.3, previous data suggest that financial incentives are effective for promoting complex healthy behaviors such as quitting smoking³⁹⁻⁴¹. Further, we believe that incremental (modest) incentives are likely to significantly increase screening completion. First, we assumed that a 10% or more difference in initial screening participation would be clinically meaningful. Second, we assumed that the screening completion rate associated with the \$5 group would be 43%, and that the rate for the \$10 group would be at least 53%. The 43% rate was chosen because our response to FIT invitations with our prior outreach program was 33%, and we would consider a 10% or more increase Version 8, June 29, 2015

in screening completion associated with the \$5 intervention over organized outreach alone to be clinically meaningful. Similarly, the 53% rate was chosen for the \$10 group because we would consider a 10% or more increase in screening completion associated with the \$10, rather than the \$5 group to be clinically meaningful. Under these assumptions, with an alpha=0.05, we estimated 1090 patients (n=545 in the \$5 group and n=545 in the \$10 group) would be required for 90% power to detect a statistically significant difference of 10% or more in initial screening participation. Because we recognize uncertainty in the estimating the expected difference between the two groups, and because we wanted to increase our ability to conduct exploratory comparisons of repeat FIT participation rates associated with the \$5 and \$10 groups, we increased the planned sample receiving financial incentives to 2,000 (n=1,000 in the \$5 group and n=1,000 in the \$10 group). Thus, we will have more than enough power to detect differences of 10% or more in initial screening participation.

Evaluation Aim D) Assess all CPRIT required outcomes, including increase in early stage cancer detection from baseline, as well as systems changes required to boost screening. To assess increase in early stage cancer detection from baseline, we will compute proportion of CRC patients with early stage cancer at baseline and at end of Year 3. JPS Cancer Registry data will be used for this computation. Rate of early stage cancer will be defined as:

Early Stage	# CRC patients with SEER Summary

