Secondary analyses. We plan to conduct several secondary analyses. First, we recognize that results from Evaluation Aim A, in which baseline screening rates will be compared to follow up screening rates at year 3, could be confounded by time trends in CRC screening rates, which generally have been increasing over time. Accordingly, we will compare the observed rate of CRC screening in Year 3 to the expected rate of CRC screening based on time trends in screening at JPS. The expected rate will be estimated using the secular trend for CRC screening using annual screening rates for each of the 7 years 2006-2011 prior to start of our prevention program in 2012. All rates will be standardized by gender and age strata (50-54, 55-59, and 60-64 years) to the population distribution of men/women and these age strata for 2012, and a standardized incidence ratio (SIR) will be computed. An SIR greater than 1, with an associated 95% confidence interval that does not cross 1 will be interpreted as evidence to support impact of our outreach intervention beyond time trends in CRC screening rates. We have previously used this approach to assess impact of a University of Texas health plan policy that waived copays for colonoscopy screening on CRC screening rates which began in 2009, in which we compared colonoscopy uptake 2002-2008 to uptake after policy institution⁴⁶.

Version 8, June 29, 2015

Second, to identify factors independently associated with screening outcomes, we will construct several logistic regression models. For example, to identify predictors of initial screening completion, we will create a model using initial screening completion rate as the primary outcome (dependent) variable, and several potential predictors of completion. Predictors considered for model inclusion will include age, sex, race/ethnicity, frequency of primary care visits, exposure to the screening outreach program, and exposure to financial incentives. A similar model will be created with the outcome of programmatic screening as the dependent variable. For these exploratory analyses, 2-sided p values of 0.05 will be considered statistically significant.

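### Sub-study Part 1 rests on an unexplained two-sided alpha of 0.125 per comparison, its only stated significance level, while the rest of the protocol uses 0.05

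*Combined protocol and SAP*

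**What the plan says.** The protocol (Sub-Study Procedures, rationale and plan for part 1) tests three invitation letters in 2,124 people: "individuals will be randomly assigned 1:1:1 to each condition". With a 36% response to the control letter and 708 per group, it says "we will have over 80% power to detect absolute increases of" 8 percentage points or more for each alternate letter against control, "assuming two-sided alpha=0.125 for each comparison".

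The Part 1 text names no test, no p-value threshold and no rule for handling two comparisons. The Biostatistics section does not mention the sub-study.

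Elsewhere the level is always 0.05. The next power statement, for Part 2, reads "assuming two-sided alpha=0.05, we will have 80% power to detect a difference post intervention of" 14.9 points or more. Evaluation Aims A to D use 0.05, and so do the exploratory regression models under Secondary analyses: "2-sided p values of 0.05 will be considered statistically significant".

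**The concern.** A level of 0.125 is two and a half times the 0.05 used everywhere else, so a randomised comparison is planned at a looser level than the exploratory models. No reason is offered, and the value looks like a slip for 0.025 or 0.0125.

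The figure sits in a power statement, where a wrong alpha would normally affect only the power wording. Part 1, however, has no other threshold to fall back on. An analyst must either apply 0.125 or choose a level later, possibly after seeing results. If 0.125 is applied to both comparisons, the risk of declaring an ineffective letter successful is well above what the rest of the protocol accepts for a single test.

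**Working it through.** **Inputs** (Sub-Study Procedures, part 1): control response 36%; alternate 44% (36 + 8 points); 708 per group (2,124/3 = 708); two comparisons sharing one control group.

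**Power formula** (two-proportion z-test, pooled variance under the null):

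- Mean proportion = (0.36 + 0.44)/2 = 0.40.
- Null SE = √(2 × 0.40 × 0.60/708) = 0.02604.
- Alternative SE = √((0.36 × 0.64 + 0.44 × 0.56)/708) = √(0.4768/708) = 0.02595.
- Power = Φ((0.08 − z × 0.02604)/0.02595), where z is the two-sided critical value.

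**The plan's own figure.** At 0.125, z = 1.534 and power = Φ(1.544) = 93.9%. The statement of over 80% is therefore true, but 93.9% is far from 80%.

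**Candidate levels.** The number per group for 80% power is (z√0.48 + 0.8416√0.4768)²/0.08². The smallest significant gain assumes an observed control rate of 36%.

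| Two-sided alpha | z | Power, 708 per group | n per group for 80% | Difference detectable at 80% | Smallest significant observed gain |
|---|---|---|---|---|---|
| 0.125 | 1.534 | 93.9% | 423 | 6.2 points | 4.0 points |
| 0.05 | 1.960 | 86.8% | 588 | 7.3 points | 5.1 points |
| 0.025 | 2.241 | 79.8% | 712 | 8.0 points | 5.8 points |
| 0.0125 | 2.498 | 71.8% | 835 | 8.7 points | 6.5 points |

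A simulation of 1,000,000 trials gave power of 93.7%, 86.6%, 79.6% and 71.7%.

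**Alpha implied by exactly 80% power.** Solving the formula for alpha gives 0.0255 with pooled variance, 0.0250 unpooled and 0.0293 with a continuity correction.

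**Which formula the protocol uses.** It is not consistent.

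- Part 2 (329 versus 107, 58% baseline, alpha 0.05, 80% power) gives 14.89 points uncorrected and 15.48 corrected; the stated 14.9 matches the uncorrected formula.
- Aim C (43% versus 53%, alpha 0.05) gives 523 per group uncorrected and 543 corrected. The stated 545, which "would be required for 90% power to detect a statistically significant difference of 10% or more in initial screening participation", is closer to the corrected one.

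Either formula puts the implied Part 1 alpha near 0.025 to 0.03.

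**Error over the two comparisons, if the level were the test threshold and neither letter worked.** With equal groups and a shared control, the two z-statistics have correlation 0.5. The bivariate normal distribution then gives:

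| Two-sided alpha per comparison | At least one false rejection, either direction | At least one false claim of benefit |
|---|---|---|
| 0.125 | about 22% | about 11% |
| 0.05 | about 9.1% | about 4.5% |
| 0.025 | about 4.6% | about 2.3% |
| 0.0125 | about 2.4% | about 1.2% |

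A simulation of 1,000,000 three-arm null trials agreed to within about 0.3 percentage points.

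**The case against.** The strongest reply is that nothing in the sentence is false. Power at 0.125 does exceed 80%, and the protocol uses power figures as loose lower bounds elsewhere. For Aim A it says "we will even have 90% power to detect a smaller screening rate increase of" 5 points or more, yet 39% versus 44% with 20,000 at each time point has power above 99.99%. The group size may simply follow from the two invitation rounds (2,124/3) rather than from a power calculation, so back-solving for alpha is weak evidence. At 0.025 the power is 79.8%, so the wording would have to lose the word over; at 0.05, the level used elsewhere, the sentence would be true as written (86.8%). The protocol states no family-wise error target, and the 22% arises only if a power assumption becomes the decision rule. Part 1 is also an add-on.

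Most of this stands. The documents do not prove a misprint, cannot settle 0.025 against 0.05, and make the error-rate consequence conditional. What it does not answer is that 0.125 is unexplained, differs from every other level in the protocol, and is the only level Part 1 has. Those points do not depend on the power inequality being false.

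**Conclusion.** The concern holds. The Part 1 level is unexplained, out of line with the rest of the protocol, and unsupported by any stated test or threshold. Two-sided 0.025 per comparison fits the plan's own figures best, and 0.0125 per side is the same test, so a dropped zero in a one-sided value is another possible origin. This is an inference, and the intended value is for the authors to confirm.

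If 0.125 is only a misprint in a power assumption, the effect is confined to the power wording. If it became the threshold for both tests, the chance of at least one false rejection would be about 22% (about 11% for false claims of benefit), and an observed gain of 4.0 points over 36% would count as significant, against 5.8 points at 0.025. These figures assume the planned 708 per group, a 36% control response and no effect of either letter for the error rates. The main evaluation aims are not touched. It should be fixed, but it is not a threat to the trial as a whole.

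**What to change.** Before Part 1 outcomes are analysed, confirm the intended level, name the test, state the level as the Part 1 decision threshold, and make the power sentence agree:

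- **Two-sided 0.025 per comparison (0.05/2).** This fits the plan's figures best and holds the two-comparison error within 0.05. Change over 80% to about 80% (79.8%).
- **0.05 per comparison.** State power of about 87% and a two-comparison error of about 9%.
- **Two-sided 0.0125.** This could arise as 0.05/4 if both outcomes in the Part 1 hypothesis (that the added information "will further increase FIT and follow-up response rates") are to be tested, although power is given only for letter response. State power of about 72%, or a detectable difference of 8.7 points.
- **0.125 retained.** Give the reason and state the two-comparison error of about 22%.

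The cost is one or two sentences in the protocol. No additional patients or data are needed.

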Data Sources and Data Tracking. *Our approaches to data acquisition, as well as data tracking have been previously developed and previously used to evaluate CRC screening rates and deliver screening.* The primary data source used to identify patients eligible for our outreach program will be JPS administrative claims database and Epic electronic medical record. At baseline, these data will be queried to identify all 50 to 64 year old patients potentially eligible for program inclusion. Demographic data, such as sex and race/ethnicity, as well as visit data, such as dates of any health system visits and any associated CPT codes with health system visits will be extracted and analyzed to determine which patients are eligible and up-to-date with screening. Data required for inviting patients to screening and tracking follow up, such as names and addresses, will be imported into a tracking database that has been previously developed and tested for this purpose. The tracking database facilitates all day to day program activities and associated data collection. For example, daily, a report is generated of patients who have been mailed FIT, and are due for follow up phone reminders to complete the FIT and return it. The database also allows for updating patient results, such as results of FIT and colonoscopy tests.

Sub-Study Procedures:

A sub-study will be conducted with the goal of identifying strategies that may further increase rates of 1) initial participation in colorectal cancer screening, and 2) follow up of abnormal colorectal cancer screening tests with colonoscopy. This sub-study involves 2 parts:

Part 1) Participants scheduled to receive mailed fecal immunochemical test (FIT) outreach for the first time late in the 2nd year of the study (currently ongoing) will be randomly assigned to receive one of three invitation letters, which vary slightly from one another. These letters represent small, but potentially impactful modifications to our original invitation letters.

All participants randomized to the original \$5 and \$10 incentive groups were enrolled during Year 1 of the study. After the incentive groups reached full enrollment, all new participants received the Version 8, June 29, 2015 11

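### Sub-study Part 2 credits the pre-post change in colonoscopy follow-up to the red envelope, but the comparison measures envelope, new invitation letters and calendar time together, against a pre group that is not defined

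*Combined protocol and SAP*

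**What the plan says.** All references are to the combined protocol and SAP.

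- **Part 2, envelope.** Sub-Study Procedures, Part 2, sends abnormal FIT results in a red envelope and normal results in a white one. It adds: "The only change to this portion of the study is the color of the envelope patients receive".
- **Part 2, analysis.** The rationale for Part 2 intends to "conduct an pre-post analysis of the follow-up rates to test our hypothesis that this alerting tactic will increase follow-up rates". For the size of the comparison, "pre-intervention, we assume there are at least 329 individuals with abnormal FIT", of whom 58% (191) complete colonoscopy. At least 107 patients are expected afterwards. The stated detectable difference is 14.9 points at 80% power, two-sided alpha 0.05.
- **Part 1, letters.** For new participants in two predetermined rounds (2,124 people), "the standard invitation letter will be replaced with one of the 3 modified letters", randomised 1:1:1. Part 2 also places its change in two predetermined rounds. Letter (i), the control, is "similar to letters in previous studies with some slight wording and grammatical improvements". Letter (ii) adds the value of the test. Letter (iii) also has "a sentence assuring patients that should a follow-up test be requested, it will be provided free of charge". The stated hypothesis is that giving the value of the kit and "attenuating concern about future cost will further increase FIT and follow-up response rates".
- **Who is in the post rounds.** By the Part 1 text they are people receiving "outreach for the first time late in the 2nd year of the study". The $5 and $10 groups were enrolled in Year 1, and new participants since then have had the standard, non-incentive invitation.
- **Follow-up time.** Screening Completion Follow Up runs to the end of Year 3 for everyone. The section on guideline-based follow up sets a goal of scheduling colonoscopy within 12 weeks of the abnormal FIT.

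**The concern.** A pre-post test can credit one cause only if nothing else relevant changed between the periods. Here the invitation letter changes for everyone in the post rounds, and the plan's own hypothesis makes letter content a second possible cause of better follow-up. Randomising the letters does not separate the two, because every post patient with an abnormal result gets the red envelope whichever letter came first.

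Two definitions that would make the periods comparable are also missing.

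- **Pre group.** It may include Year 1 incentive patients or patients on a repeat FIT, while the post group, by the Part 1 text, includes neither.
- **Completion window.** The only stated follow-up rule is a calendar end, which gives earlier patients longer to complete colonoscopy than later ones.

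At stake is the conclusion that JPS would draw about the envelope. A letter or time effect could be credited to it, or a real benefit could be understated.

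**Working it through.** **Method.** Two-proportion z test with pooled null variance:

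power = Φ[(p2 − p1 − 1.96 × SE0) / SE1], where SE0 = √[p̄(1 − p̄)(1/n1 + 1/n2)] and SE1 = √[p1(1 − p1)/n1 + p2(1 − p2)/n2].

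**1. The plan's own figure.** Inputs from the rationale for Part 2: n1 = 329, n2 = 107, p1 = 0.58, p2 = 0.58 + 0.149 = 0.729.
- p̄ = (329 × 0.58 + 107 × 0.729)/436 = 0.617; SE0 = 0.0541; SE1 = 0.0509.
- Power = Φ[(0.149 − 1.96 × 0.0541)/0.0509] = 80.1%. The stated 14.9 points reproduces.

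**2. Does the 107 pool over letters?** The plan does not say. 107/(2,124 × 0.36) = 14.0% abnormal, so 107 fits the whole of both rounds at the 36% return rate if about 14% are abnormal. One letter arm would supply about 107/3 ≈ 36. At the 12% abnormal rate quoted from the prior program, the rounds would give 2,124 × 0.36 × 0.12 = 92. Pooling is therefore an inference, though the natural one.

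**3. Letters alone, no envelope effect.** The documents give no letter effect on colonoscopy, so these are assumptions. If only letter (iii) acts, the pooled post rate moves by one third of its effect.

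| Assumed effect of letter (iii) | Pooled shift | Two-sided false-positive rate |
|---|---|---|
| 5 points | 1.7 | 6.0% |
| 10 points | 3.3 | 9.2% |
| 14.9 points | 5.0 | 14.5% |

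**4. Letters acting the other way.** Suppose letters (ii) and (iii) raise FIT return from 36% to 44%, the 8 points used in the Part 1 power statement. Then 16/(36 + 44 + 44) = 12.9% of post returners are extra, assuming an equal abnormal rate. If those extra patients complete colonoscopy 10 points less often (assumed), the pooled rate falls 0.129 × 10 = 1.3 points and power for a true 14.9-point gain falls to 72%.

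**5. Unequal time.** If 99% of post completions are captured (assumed) and all pre completions are, the observed post rate is 0.729 × 0.99 = 72.2% and power is 76%.

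**6. Pre group.** If all 2,000 incentive patients were in it, at 36% return and 12% abnormal (assumed to apply to them), they supply 2,000 × 0.36 × 0.12 = 86 patients. Removing them leaves 329 − 86 = 243. With the 58% baseline held, the detectable difference rises from 14.9 to 15.5 points.

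**7. Follow-up by letter within the post period.** With 36 v 36 at a 58% base, the detectable difference is about 29 points.

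**The case against.** The strongest reply has four parts.

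- **The only-change sentence.** A reader might infer that it is false. It is not: it is limited to this portion of the study, meaning the result mailing, and Part 1 describes the letter change openly. What fails is the step from that sentence to crediting the whole difference to the envelope.
- **A large letter bias.** A reader might infer one. Nothing in the documents supports it. Colonoscopy is already free (Potential Risks), abnormal-FIT patients are called within 1 week, and the higher false-positive rates above need large effects from one sentence in an earlier letter. The sign is also open. This part stands.
- **Severe loss from unequal time.** A reader might infer this too. If only 90% to 95% of post completions were captured, power would be 28% to 55%. Those rates are hard to square with invitations late in Year 2, follow-up through Year 3, and a 12-week scheduling goal that the prior program met for all willing patients. Post patients probably have about a year. This part stands as well.
- **Post-group composition.** It is taken from the Part 1 text; Part 2 says only participants. That is fair, and the matching step below depends on it.

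The reply leaves the attribution problem and the missing definitions in place. The time-trend analysis under Secondary analyses covers Aim A only.

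**Conclusion.** The point holds as a minor one. The planned test estimates the combined effect of envelope, letters and calendar time, and 14.9 points is the detectable difference for that combination only. The figure itself is correct. The pre group and the completion window need definition before the two periods can be called comparable.

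The likely bias is modest and could go either way. The letter effects, the capture rate and the count of 86 incentive patients are assumptions, not document values. Pooling over letters, an even split of the 107 and the first-time, non-incentive make-up of the post group are inferred from the text. The sub-study is secondary, and Aims A to D are not affected.

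**What to change.** 1. Keep the 329 v 107 test, but label it the combined effect of envelope and letters. Report it as exploratory and unable to exclude a time trend.
2. Define the pre group by stated rounds and dates. Restrict it to first-time, standard-letter, non-incentive invitees, and restate its size, the 58% baseline and the detectable difference.
3. Count colonoscopy completion within one identical analysis window from the abnormal FIT in both periods. Fix its length before analysis, as one that every post patient can reach before data close. The table of variables already includes test completion dates.
4. Report follow-up by randomised letter within the post period, as estimates with confidence intervals, to show whether letters affect follow-up. Comparing the pre group with letter (i) alone would not isolate the envelope: that letter is also reworded, calendar time stays confounded, and with about 36 post patients it detects only about 22.8 points.

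**Cost.** Analysis wording only, with no new patients or procedures. The matched pre group may be smaller and its detectable difference slightly larger (about 15.5 points in the example). The by-letter comparison is imprecise (about 29 points). A time trend remains. Randomising envelope colour would remove it, but 54 v 53 patients detect only about 24.5 points, so it is not proposed.
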